Our study will evaluate the efficacy of ganciclovir ophthalmic gel 0.15% in the treatment of herpes zoster keratitis that results from HZO.

A. Background and Significance of Proposed Research

The cornea is involved in approximately 65% of patients who develop HZO. In a study analyzing the corneal complications of HZO in 93 patients, Liesegang found punctate epithelial keratitis in 51%, early pseudodendrites in 51%, anterior stromal infiltrates in 41%, neurotrophic keratitis in 25%, late corneal mucous plaques in 13%, exposure keratitis in 11% and disciform keratitis in 10%. He suggested that initial corneal lesions were likely due to direct damage from the viral infection, whereas the later sequelae were the result of vasculitis, immune reactions to the viral antigens, delayed hypersensitivity reactions, or damage to the nerves and tissue.⁴

Piebanga and Laibson described some of the late corneal disease associated with HZO, including a chronic epithelial keratitis that was characterized by epithelial mucous plaques, which has also been termed mucous plaque keratitis (MPK). The onset was typically months after the initial presentation. Pavan-Langston et al performed polymerase chain reaction studies on an excised corneal button and observed the response of 4 patients to antiviral therapy. They demonstrated successful use of topical trifluridine, vidarabine, and oral acyclovir individually in different cases.⁵ The use of newer topical and oral antivirals may improve the general success rate of treatment.

Late-stage stromal keratitis can occur months after the initial onset of the zoster corneal infection.⁶ This condition is characterized by deep stromal inflammation, which presents as a typical disciform lesion or asperipheral keratitis. Corneal edema

may be associated with these lesions. If these lesions are not treated with corticosteroids, a chronic inflammation may develop that leads to neovascularization, scarring, and ulceration of the cornea. Later, lipid deposition may occur. Corticosteroids are used to treat the inflammatory component of these disorders.

Neurotrophic keratitis develops due to VZV affecting the sensory nerves and causing hypoesthesia, which leads to the deterioration of corneal epithelium and a punctate keratopathy. If the epithelial breakdown progresses, large corneal epithelial defects occur. Sterile corneal ulcerations occur that may also become secondarily infected. If untreated, the cornea may become opaque, progressively thin, and may eventually perforate.

For the purposes of our study, we define zoster dendrite as a stuck-on rod shaped or branching lesion without terminal bulbs and not a corneal melt, keratouveitis, sclerouveitis, or corneal erosion related to neurotrophic keratitis.

Ganciclovir ophthalmic gel

Ganciclovir ophthalmic gel 0.15% was approved by the Food and Drug Administration (FDA) in September 2009 for the treatment of acute herpetic keratitis (dendritic ulcers). The results of three pooled phase II studies and one phase III trial demonstrated similar cure rates of ganciclovir ophthalmic gel 0.15% compared to acyclovir ophthalmic ointment 3% at day 7. Ganciclovir ophthalmic gel 0.15% demonstrated non-inferiority compared to acyclovir ophthalmic ointment 3%. Of note, acyclovir ophthalmic ointment is not commercially available in the United States and there are no head-to-head clinical trials of ganciclovir ophthalmic gel compared to trifluridine 1% ophthalmic solution for the treatment of acute herpetic keratitis. Ganciclovir ophthalmic gel 0.15%, has not been studied in patients with stromal keratitis.

Previous trials have shown that topical antivirals have been ineffective in the treatment of herpes zoster keratitis. However, there have been a few unpublished reports of use of Zirgan for herpes zoster keratitis (http://www.revoptom.com/content/c/24774/).

Viral plaque reduction assays have been used to test ganciclovir's antiviral activity in vitro, and ganciclovir was found to be a powerful inhibitor of viral replication for HSV1, HSV2, HZV, EBV, CMV, and HHV6 viruses. The GCV 0.15% strength was adopted on the basis of preclinical studies in experimental animal models of herpetic keratitis, preclinical and clinical pharmacokinetic distribution studies, and controlled clinical trials. The gel formulation allows for even distribution of the active drug, prolongs contact with the cornea better than an ointment, and provides greater efficacy at a concentration of 0.15%. The pH (7.45) and osmolarity (300 osmoles) of Ganciclovir gel 0.15% are close to normal physiological values.

In an experimental model of herpetic keratitis in rabbits ganciclovir ointment demonstrated antiviral activity at a concentration of 0.1% with no positive ocular viral samples after 5 times a day treatment at 12 days and at 14 days when applied 3 times a

day. Using this same mode, Castela et al. 8 showed that ganciclovir gel at concentrations of 0.2%, 0.05%, and 0.0125% applied 4 times a day for 12 days, starting on day 3 after infection, effectively treated herpetic keratitis. Ocular isolates showed no positive viral samples on day 12 with GCV 0.2% and 0.05%, and on day 14 with GCV 0.0125%.

Pharmacology/Pharmacokinetics of Ganciclovir

Ganciclovir is activated to ganciclovir triphosphate by viral and cellular thymidine kinases (TK). This active metabolite then inhibits DNA replication by competitive inhibition and direct incorporation into viral DNA resulting in chain termination. It is designed to work selectively by specifically targeting infected cells. Zirgan is a prodrug that is phosphorylated primarily by infected cells. In contrast, the mechanism of action of trifluridine is nonselective and as a result, it is toxic to healthy cells. Also, trifluridine contains the preservative thimerosal, to which many patients have an allergic sensitivity. Zirgan is preserved with benzalkonium chloride (BAK) rather than thimerosal. While BAK has been shown to cause low-grade toxicity to ocular surface cells, this typically occurs only after long-term and/or frequent use of ophthalmic medications.

Ganciclovir has activity against Epstein-Barr virus, cytomegalovirus (CMV), adenovirus, herpes zoster, and herpes simplex virus (HSV) types 1 and 2.^{11,12} ¹³

Ganciclovir ophthalmic gel has minimal systemic absorption, with the total daily topical dose approximately 0.04% and 0.1% of oral and intravenous ganciclovir doses, respectively. Rapid penetration of ganciclovir has been demonstrated within 5 minutes with topical administration resulting in therapeutic drug levels in ocular tissue, which is imperative for the treatment of herpetic keratitis. ¹⁴

Ganciclovir ophthalmic gel 0.15% is FDA approved for the treatment of acute herpetic keratitis (dendritic ulcers). ^{13,15} This study looks at the use of ganciclovir gel for the treatment of zoster keratitis. Current available topical antiviral alternatives are trifluridine 1% ophthalmic solution and vidarabine ointment (VIRA-A Ophthalmic Ointment). Our study will provide data regarding the use of ganciclovir ophthalmic gel as an additional tool in the treatment of herpes zoster keratitis which can have potentially blinding sequelae.

Genteal Gel

Genteal gel is a non-prescription eye lubricant gel and is commonly used for treatment of dry eye, irritated eyes. There is no anti-viral agent within genteal gel.

Oral anti-viral

Acyclovir and valacyclovir are the standard treatments used in patients with herpes zoster¹⁷ to prevent long-term complications, including intraocular complications. Acyclovir and valacyclovir have not been studied as single use treatments of herpes zoster dendrites.

II. Hypothesis

We hypothesize that ganciclovir ophthalmic gel 0.15% will be an effective treatment of herpes zoster dendritic keratitis as measured by reduction of the dendritic ulcer by 90% within 2 weeks in at least 50% of subjects receiving ganciclovir while on oral anti-viral therapy compared with 0% of subjects receiving placebo while on oral anti-viral therapy.

III. Study Objectives

The purpose of this study is to evaluate the efficacy (defined as the reduction in ulcer size by 90%) of topical ganciclovir 0.15% in treatment of herpes zoster dendritic keratitis.

The investigators will enroll 33 patients with a diagnosis of HZO with corneal involvement. Their medical records will be reviewed, including their demographic data as well as ophthalmic and medical histories. Subjects will be recruited from the Department of Ophthalmology at Northwestern University (NU), as well as from the qualified practices of physician members of the Chicago Cornea Association and selected cornea practices nationwide.

IV. Study Population

A. Inclusion Criteria

- 1. Males and Females, age 18 and above who have been diagnosed with a corneal infection caused by the herpes zoster virus
- 2. Have not been on ganciclovir gel or any other form of topical antiviral therapy for the past month
- 3. Able and willing to attend subsequent follow-up visits

B. Exclusion Criteria

- 1. Associated retinitis
- 2. Patients with a known allergy to hypromellose gel, ganciclovir, acyclovir, or valacyclovir
- 3. Patients who will require systemic or intra-vitreal ganciclovir therapy
- 4. Patients who are pregnant or breastfeeding

V. Study Procedures

A. Study Design

This is a prospective, randomized, parallel group study with two arms: subjects receiving oral anti-virals as standard of care therapy while receiving either ganciclovir ophthalmic gel 0.15% (Zirgan) or a placebo ointment (genteal gel). Subjects with corneal dendritic involvement from herpes zoster will be randomized (1:1) to receive ganciclovir ophthalmic gel 0.15% gel or placebo, which will be applied to the affected eye 5 times a day for 7 days, followed by 3 times a day for an additional 7 days. At two weeks, if the zoster dendrite has not healed, rescue therapy can be performed at

the discretion of the treating physician (Zirgan, the study drug, will not be used as a rescue therapy).

Clinical examinations including a dilated fundus examination will be performed at the Screening/Baseline Visit. Subsequent clinical examinations will be performed at study visits 1, 2, and the End of Study/Early Termination Visit, however, fundus examinations are not completed at subsequent examinations. Two sets of slit lamp photographs will be obtained at each visit.

Slit-lamp photographs can be obtained with fluorescein or Rose Bengal staining; however the same staining method should be used throughout the study. Photos will first be taken without fluorescein or Rose Bengal and then taken with fluorescein or Rose Bengal. Time to reduction ulcer size will be recorded as the primary end point and compared among the two groups from the slit lamp photographs. Slit lamp photographs will be reviewed by a qualified physician, who will be masked to the patient information and the study drug received. Intraocular pressure (IOP) measurement will be performed at each study visit and subjects will receive numbing eye drops prior to the IOP.

Both groups will receive the standard 7-day oral therapy of acyclovir (800 mg po five times daily), valacyclovir (800 mg po five times daily), or valacyclovir (1000 mg po three times daily). This oral anti-viral treatment is being given as standard treatment for herpes zoster to prevent long-term complications, including intraocular complications. If the treating physician feels strongly about an altered dosing regimen, this is allowed as long as it is reported. A topical steroid will not be administered unless there is associated inflammation.

	Screening/ Baseline Visit (Week 0)	Study Visit 1 (Week 1)	Study Visit 2 (Week 2)	End of Study Visit/Early Termination Visit (Week 3)		
Informed consent	X					
Medical history	X	X	X	X		
Dilated fundus examination	X					
Eye exam	X	X	X	X		
IOP	X	X	X	X		
Slit lamp photos	X	X	X	X		
Oral antiviral dispensed	X					

Study drug dispensed	X			
Diary reviewed		X	X	

The study drug will be sent to the study doctor in a sealed container that should be opened by the patient at home. Patients will be required to fill out a dosing diary. The dosing diary and the remaining drug must be returned to the NU study site from all participating sites.

A Coded Identifier List (CIL) will contain the subject's name, subject's medical record number, subject's date of birth, and the Study ID Number assigned by the study staff. The CIL will be stored on a secure server, be password protected, and will be maintained by authorized study personnel. Once a subject has been given a Study ID Number, all data collected will be identified through this Study ID Number. Each site will maintain their own Coded Identifier List and Northwestern University will not have access to each site's CIL.

B. Study Drug

Ganciclovir ophthalmic gel 0.15%: Sufficient quantity for 15 eyes. The subjects will put the study drug into affected eye(s) 5 times a day while awake for 7 days, followed by 3 times a day while awake for 7 days, or until healing of corneal ulcer. Clinical examinations will be performed at the Screening/Baseline Visit and study visits 1, 2, and the End of Study/Early Termination Visit.

The drug and placebo will be randomized and distributed to the participating centers that will not have access to the drug by Northwestern University study staff. The study drug will be stored and maintained by the Department of Ophthalmology at Northwestern Memorial Hospital located at [name].

C. Subject Compliance

In order to obtain reliable safety and efficacy data, it is critical that each subject complies with the dosing schedule specified in this protocol. Each subject will be given a dosing diary to fill out every time they apply the study drug or placebo. Subjects must also continue with the intake of their systemic medications prescribed.

D. Randomization and Masking

We anticipate enrollment of 33 patients. The study groups will be assigned in a 1:1 ratio, with expected non-completion rate of 10% this will give us 15 patients per treatment group. Neither the patient nor the study doctor or study staff will be able to pick which study group the patient is in or know which study group the patient is in. If subjects have an infection in both eyes, only on eye will be randomized to receive either Zirgan or placebo. The other eye will be given standard of care treatment.

Subjects will be randomized to receive ganciclovir gel (Zirgan®) versus hypromellose gel (Genteal Gel®; Placebo) to be applied topically. A computer algorithm for random number generation will be used to generate the treatment assignments. The study is double-masked and all site investigators, study staff, and subjects will be masked to the group to which subjects are randomized. Masked study doctors at Northwestern University will be reading all slit lamp photos, including those from the other participating sites. The study staff that will be dispensing the study drug and placebo will also be masked.

E. Rescue Therapy

Rescue therapy is defined as any treatment that would have a therapeutic effect on the herpes zoster keratitis. Rescue therapy will be offered if progressive corneal thinning, corneal inflammation, or worsening of the dendritic keratitis occurs. All uses of rescue therapy will be deemed medically necessary by the site investigator.

If rescue therapy is needed after a subject has treatment failure, the site investigator must report the treatment failure and the type of rescue therapy used to the lead site. The lead site study staff can be reached by calling [contact].

VI. Risks and Benefits

A. Risks

Ganciclovir ophthalmic gel 0.15%

Most common adverse reactions reported in patients were blurred vision (60%), eye irritation (20%), punctate keratitis (5%), and conjunctival hyperemia (5%). ¹⁶

Dilated fundus examination

The dilation medicine will cause some minor stinging after being placed in the eye. The dilation will cause light sensitivity and blurry vision for 4-6 hours.

Slit lamp photography

Bright flashes may cause discomfort to the subject.

Intraocular pressure (IOP) measurement

Numbing eye drops (proparicaine 0.5% ophthalmic solution) will be used prior to taking subject's intraocular pressure. These eye drops may cause redness and stinging. During the measurement, the study doctor will use a machine that touches the surface of the eyes. In rare circumstances, this machine could scratch the subjects' cornea. Such scratches are usually self-heal in less than 24 hours.

The potential harm to the subjects is loss of privacy and confidentiality. Indirect identifiers will be used to link data obtained from different methods. The key will be stored separately from the data and will be destroyed after data collection has been completed.

B. Benefits

Subjects' herpes zoster keratitis may get better as a result of the use of ganciclovir gel. The knowledge gained from this study may benefit future patients with this condition.

VII. Statistical Considerations

A. Sample Size Justification

We will recruit 33 patients in order to account for drop-out or non-completion rate of 10%, providing approximately 15 patients per treatment group.

With 15 patients per group we have sufficient power to test H:p1=p2 vs H1: p1>p2 with type 1 error of 5%, when true values of p1=55% and p2=5%. See below.

Two Independent Proportions (Null Case) Power Analysis Numeric Results of Tests Based on the Difference: P1 - P2 H0: P1-P2<=0. H1: P1-P2=D1>0. Test Statistic: Fisher's Exact test

Sar	nple	Sample	Prop H1	Prop				
	Size	Size	Grp 1 or	Grp 2 or	Diff	Diff		
G	rp 1	Grp 2	Trtmnt	Control	if H0	if H1	Target	Actual
Power	N1	N2	P1	P2	D0	D1	Alpha	Alpha
]	Beta							
0.9978	30	30	0.5500	0.0500	0.0000	0.5000	0.0500	0.0022

B. Statistics

We will use descriptive statistics to present the data in a convenient fashion, including graphics. Success rates in two treatment groups will be compared using Fisher's Exact test. 95% Confidence intervals for rates in each of the treatment groups will also be provided.

VIII. Ethical Considerations

A. Data Disclosure and Subject Confidentiality

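### The allergy exclusion does not cover the other components of the study gels, although the protocol names benzalkonium chloride as the preservative in the ganciclovir gel

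*Combined protocol and SAP*

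**What the plan says.** Section IV.B (Exclusion Criteria) has four numbered items: retinitis, allergy, need for systemic or intravitreal ganciclovir, and pregnancy or breastfeeding. The allergy item reads, in full, "Patients with a known allergy to hypromellose gel, ganciclovir, acyclovir, or valacyclovir". The available text contains no general clause on excipients and no clause that lets the investigator exclude a patient on judgement.

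The pharmacology part of the background states that "Zirgan is preserved with benzalkonium chloride (BAK) rather than thimerosal". Just before, it says of the alternative topical drug that "trifluridine contains the preservative thimerosal, to which many patients have an allergic sensitivity". For benzalkonium chloride itself it mentions low-grade surface toxicity, typically after long-term or frequent use. It does not mention allergy to it.

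Section V.A has the gel "applied to the affected eye 5 times a day for 7 days, followed by 3 times a day for an additional 7 days". Section V.B adds that treatment may stop when the ulcer heals. Under V.A and V.D the gel is double-masked and supplied against a hypromellose placebo gel. The text following the visit schedule says that it arrives in a sealed container that the patient opens at home.

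**The concern.** An allergy exclusion exists to keep out patients who are already known to react to something the trial will give them. Here the protocol names an ingredient of its active gel in one section and leaves it out of the allergy criterion in another. It also treats sensitivity to a preservative as a relevant drawback of a competing drug, so this kind of risk was in view when the protocol was written.

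A patient who reports at screening a known allergy to benzalkonium chloride meets every written criterion. Because the product is masked and sealed until it reaches the patient's home, the site doctor cannot count on seeing the product label as a second check. The written criterion therefore matters more than it would in an open-label study. What is at stake is an avoidable reaction in the affected eye of a patient whose allergy was known beforehand.

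**Working it through.** The plan states no figure on this point. The check sets the sections side by side and counts the exposure.

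**Substances in the gels against the allergy criterion**

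| Substance | Where the protocol names it | In criterion 2? |
|---|---|---|
| Ganciclovir | Throughout | Yes |
| Hypromellose gel (placebo) | V.D | Yes |
| Acyclovir, valacyclovir | V.A | Yes |
| Benzalkonium chloride | Background, pharmacology part | No |
| Placebo gel's preservative, if any | Not stated | No |

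The placebo is listed as a gel. The active treatment is listed by its drug substance alone. Nothing in the criterion extends it to the remaining ingredients of either product.

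**Exposure under the schedule in V.A, per treated eye**

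- First week: 5 × 7 = 35 applications.
- Second week: 3 × 7 = 21 applications.
- Full course: 35 + 21 = 56 applications.

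This is a maximum, since V.B allows treatment to end at healing. The first scheduled follow-up is at Week 1, by which time up to 35 applications may have been made.

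**Examination agents**

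- Anaesthetic: V.A says that "subjects will receive numbing eye drops prior to the IOP", and VI.A names the agent: "Numbing eye drops (proparicaine 0.5% ophthalmic solution) will be used prior to taking subject's intraocular pressure". The schedule has an IOP measurement at all 4 visits.
- Dye: each photograph set includes a stained image, also at 4 visits. However, "Slit-lamp photographs can be obtained with fluorescein or Rose Bengal staining", so staining is required but neither dye is. A patient allergic to one can be photographed with the other from baseline onward, which respects the requirement to keep one method throughout.

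Criterion 2 lists none of these agents.

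**Frequency**

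The documents give no rate of allergy to benzalkonium chloride, so no expected number of patients can be calculated.

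**The case against.** The strongest reply is that the practical gap is small.

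- Criterion 2 can be read as listing the treatments as products: the two gels, then the two oral drugs. A patient known to react to the ganciclovir product would then be excluded, leaving only those whose preservative allergy is known from another product. This narrows the gap without closing it. The reading is arguable, because the word gel is attached only to hypromellose, and several sites have to apply the criterion.
- Medical history is taken at baseline, and recruitment runs through cornea practices. A careful clinician may well ask and decline to enrol, since meeting the criteria permits enrolment and does not compel it. That stands. What is missing is the written rule.
- The anaesthetic and the dyes are routine examination agents that a clinician would handle in ordinary practice, and either dye may be used. This stands, and is why that part is optional.

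Some stronger readings are tempting, but the documents do not support them.

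- *The protocol itself warns of allergy to benzalkonium chloride.* It does not. Its allergy remark concerns thimerosal in a drug not used here. For benzalkonium chloride it mentions only toxicity, which an allergy exclusion would not address.
- *The plan knowingly exposes allergic patients.* The criteria fail to bar them. Nothing shows intent.
- *A reaction would bias the endpoint or break the masking.* The documents do not say that such a reaction stains the cornea, resembles a dendrite or reveals the allocation. They do not state the placebo's preservative, so it is unknown whether any effect would fall on one arm only. The photograph readers are masked.
- *One affected patient moves an arm's success rate by 1/15 = 6.7 points.* The arithmetic is right for 15 per arm, but it holds for any single failure or loss and does not measure this gap.

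**Conclusion.** The point holds as a minor patient-safety gap in the eligibility wording. The written criteria admit a patient with a known allergy to the named preservative of the active gel, with up to 56 applications to follow.

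This conclusion rests on two assumptions: that criterion 2 is applied as worded, by substance, and that the numbered list of four exclusions is complete. The number of patients affected is unknown and may be zero. No consequence for the endpoint, the masking, the sample size or Fisher's exact test is shown, and none should be inferred.

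**What to change.** Reconcile section IV.B with the background section. Extend criterion 2 so that it covers a known allergy to any component of either study gel, naming benzalkonium chloride, alongside the oral drugs already listed. Carry the same wording into the screening checklist used at the sites, and answer it from the medical history already scheduled at the Screening/Baseline Visit. The wording about either gel also covers the placebo, whose other ingredients the protocol does not give.

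The sponsor may add the anaesthetic and the dye to be used, but this is optional.

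The cost is one line of text, no added visit or test, and at most a few exclusions. The sample size and the analysis need no change.

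### The end point labelled primary (time to ulcer reduction) has no threshold, time limit, method, power or rescue handling; the end point that is tested and powered is a proportion

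*Combined protocol and SAP*

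**What the plan says.** - **V.A, Study Design:** "Time to reduction ulcer size will be recorded as the primary end point and compared among the two groups", read from the slit-lamp photographs. The sentence does not say how large a reduction counts, by when, or how times are compared. The visit table in V.A places photographs at baseline and at weeks 1, 2 and 3.
- **II, Hypothesis:** the outcome is "reduction of the dendritic ulcer by 90% within 2 weeks", expected in at least 50% of the ganciclovir group and 0% of the placebo group. This is a proportion.
- **III, Study Objectives:** efficacy is a 90% reduction in ulcer size, with no time limit.
- **VII.A, Sample Size Justification:** two proportions, 55% and 5%, are compared one-sided at 5% with 15 per group, using Fisher's exact test.
- **VII.B, Statistics:** "Success rates in two treatment groups will be compared using" Fisher's exact test, with a 95% confidence interval for each group's rate. Success is not defined there, and II is not cited.
- **Rescue:** V.A says "At two weeks, if the zoster dendrite has not healed, rescue therapy can be performed". V.E adds, without a time limit: "Rescue therapy will be offered if progressive corneal thinning, corneal inflammation, or worsening of the dendritic keratitis occurs". V.E also says that the site investigator "must report the treatment failure and the type of rescue therapy used to the lead site". It does not define treatment failure, and no section says how a rescued eye enters the analysis.

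**The concern.** V.A promises a comparison of times, but the plan contains no method for one: no survival method, censoring rule, hazard ratio, median or event count. The end point with a test and a power calculation is never called primary. After the data are in, either could be presented as the deciding result, and they need not agree.

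The photograph schedule adds to the problem. A time can take at most three post-baseline values, so ties are heavy. The last value, week 3, falls after V.A has allowed rescue at week 2.

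The proportion is not protected either. V.E permits rescue before week 2, so an eye that heals after early rescue could count as a success of its allocated gel.

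**Working it through.** **1. The plan's own figure.** The power table in VII.A gives 0.9978 for 55% against 5%. Enumerating two binomials with a one-sided Fisher p ≤ 0.05 reproduces 0.9978 at the table's 30 per group. At the 15 per group in the text, the same calculation gives 0.9013. Both are power for a proportion. Neither is power for a time.

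**2. What each section supplies.**

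| Section | Quantity | Reduction | Time limit | Test | Power | Called primary |
|---|---|---|---|---|---|---|
| V.A | time | none | none | none | none | yes |
| II | proportion | 90% | 2 weeks | none | none | no |
| III | efficacy | 90% | none | none | none | no |
| VII | proportion | none | none | Fisher | yes | no |

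No row is complete.

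**3. Can the two versions give different verdicts?** From the documents: 15 per arm, one-sided 5%, 55% against 5% (taken as the rates by week 2, the window in II), visits at weeks 1, 2 and 3. The log-rank test (z > 1.645) is an assumption, because the plan names no method for times.

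Weekly healing hazards that give the week 2 rates:

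- active: 1 − √(1 − 0.55) = 0.329
- placebo: 1 − √(1 − 0.05) = 0.0253

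For week 3 there are two assumed cases: the same hazards continue, or the unhealed eyes in both arms heal at one common rate. Each scenario used 100,000 simulated trials, with Monte Carlo error of at most about 0.15 percentage points.

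| Week 3 healing of unhealed eyes | Log-rank through week 3 wins | Fisher at week 2 wins | Verdicts differ |
|---|---|---|---|
| hazards unchanged | 99.1% | 90.0% | 9.2% |
| 30% in both arms | 80.8% | 90.3% | 15.2% |
| 50% in both arms | 78.1% | 90.1% | 17.5% |
| 70% in both arms | 81.0% | 90.1% | 15.2% |
| 90% in both arms | 89.0% | 90.3% | 8.8% |

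The direction changes. The share of trials won by Fisher alone is (differ + Fisher − log-rank) / 2:

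- Unchanged hazards: (9.2 + 90.0 − 99.1) / 2 ≈ 0.05%, so nearly every disagreement favours log-rank.
- Common 50% rate: (17.5 + 90.1 − 78.1) / 2 ≈ 14.8%. Log-rank alone wins 17.5 − 14.8 = 2.7%.

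With the log-rank test stopped at week 2, it wins 96% and verdicts differ in 5.9%. This remainder comes from Fisher's conservatism and the use of timing, not from week 3.

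**4. Early rescue counted as success.** Let r be the share of otherwise unhealed eyes, in both arms, that heal after rescue by week 2. Then p1 = 0.55 + 0.45r and p2 = 0.05 + 0.95r. Exact one-sided Fisher power, 15 per arm:

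| r (assumed) | p1 | p2 | Power |
|---|---|---|---|
| 0 | 0.55 | 0.05 | 0.901 |
| 0.1 | 0.595 | 0.145 | 0.729 |
| 0.2 | 0.64 | 0.24 | 0.592 |

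**The case against.** The strongest reply is that the plan can be read as consistent. II gives a full responder definition, III repeats the 90%, and VII's 55% against 5% sits close to II's 50% against 0%. On that reading, success in VII is the outcome in II, and only a cross-reference is missing. This is a fair guess at what was meant. It still yields a proportion, which V.A does not call primary, and III drops the time limit.

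On rescue, V.E speaks of rescue after treatment failure and requires the failure to be reported, which suggests that a rescued eye is a failure. That is the more natural reading. But the term is undefined and nothing carries it into the analysis. It is also true that rescue begun at the week 2 visit because the eye is unhealed should not affect a week 2 result. Only earlier rescue under V.E would.

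On size, the 15% to 18% figures depend on a common week 3 healing rate that no section supports. With both tests stopped at week 2, disagreement is about 6% and runs one way. Equal rescue healing in both arms dilutes the difference and so works against the drug. The figures above also assume that the drug works. Under the null (equal week 2 healing of 5% to 50%, week 3 hazard unchanged or 50%, all assumed), claiming success if either test wins gives a false-positive rate of 3.2% to 6.2%. That compares with 0.3% to 2.1% for Fisher alone, so the excess over the nominal 5% is small. These points limit the numbers, but they do not identify which result is primary.

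**Conclusion.** The concern holds and must be fixed. No end point in the plan is at once labelled primary, defined, tested and powered, and no rule covers rescued eyes in the analysis. This follows from the text alone and needs no simulation.

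The choice matters: verdicts differ in about 6% of trials if both analyses stop at week 2, and in 9% to 18% if times run to week 3. These figures rest on the protocol's rates, an assumed log-rank test and assumed week 3 healing. The power losses from early rescue rest on assumed shares of 10% and 20%. The time end point is not shown to be underpowered; its power is not stated and cannot be derived from the documents.

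**What to change.** Replace the primary end point sentence in V.A with text such as:

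> The primary end point is success: a decrease of at least 90% from baseline ulcer size, on masked reading of the slit-lamp photographs, at or before the week 2 visit. A subject given rescue therapy before reaching this decrease is counted as not a success. Groups are compared as in VII.B.

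Use the same definition of success in VII.A and VII.B. Time to 90% reduction can remain as a secondary, descriptive end point through week 2. Building VII around time to 90% reduction would also reconcile the text, but it would need a new method and power calculation; the wording above uses II's definition and VII.B's test.

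Under this wording, an eye that reaches 90% at week 1 and relapses by week 2 is a success, which the sponsor should confirm is intended. The treatment of a missing week 2 photograph still has to be stated, given the 10% non-completion expected.

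The cost is wording in V.A and VII, plus recording the date of rescue alongside the report V.E already requires. Time to reduction loses primary status. No patients, visits or photographs are added, and no treatment or rescue rule changes. The change should be made before unmasking.
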